6.6. Restrictions

- No parallel use of any other anti-head lice therapy.
- Subject agrees not to cut or chemically treat their hair while participating in the study
- Female subjects are to be informed that they must apply adequate contraceptive methods (e.g. uterine tube sterilization, sexual abstinence or vasectomized partner or combination of anti-conceptive medication and condom, spermicidal products, diaphragm, temperature method).
- Subjects agree not to use any other anti-lice treatment for the duration of the study.

6.7. Time and Events Table

The actual date and time should be recorded for all procedures and the Investigator should make every effort to perform procedures as required by the protocol.

VISIT NUMBER	Visit 1			Visit 2	Visit 3	Visit 4
VISIT DAY	Day 0			Day 1 ± 3 hrs.	Day 7 + 1d	Day 10 +2d
VISIT NAME	Screening visit (baseline)			Evaluation Visit	Second treatment	Final Evaluation
	-1H	0	+1H			
Informed Consent	X					
Demographics (ethnic group, gender, age, hair length, height...)	X					
Medical history and medication usage	X					
Concomitant medication usage during study				X	X	X
Vital signs (blood pressure, pulse, respiratory and temperature)	X			X	X	X
Urine pregnancy test – child bearing potential	X					X
Physical examination of the scalp to verify head lice infestation by study staff	X					
Inclusion/exclusion	X					
Randomization study product		X				
Skin irritation – baseline assessment prior to treatment by blinded study staff	X				X	
Ocular irritation – baseline assessment prior to treatment by blinded study staff	X				X	
Application of study medication by unblinded study staff		X			X	
Global tolerability assessment by blinded study staff and subject						X
Local tolerability assessment (subjective symptoms: burning, paraesthesia, pruritus)	X		X	X	X	X
Skin and scalp irritation –by blinded study staff		X	X	X	X	X
Ocular irritation – post treatment assessment by blinded study staff		X	X	X	X	X
Adverse Events – questioning by blinded staff			X	X	X	X
Check of restrictions				X	X	X
Questioning on satisfaction with the esthetical effect			X		X	
Discharge from study						X

7. INVESTIGATIONAL PRODUCTS

7.1. Labeling

Both test products will be labeled as shown below.

7.1.1. Product 1 (Elimax Ultra®)

Sponsor: OYSTERSHELL

Principal Investigator: [name]
 [contact] in case of emergency:
 Clinical trial ref.: OYS007-0017

Subject n#:

Use / zone: Topical use on hair and scalp

Posology: First treatment: D0; second treatment: D7

Storage: room temperature, keep away from light, close bottle tightly, **shake well before application.**

For personal use

Term	Percentage
GMOs	~10%
Organic	~85%
Natural	~75%
Artificial	~35%
Organic	~80%
Natural	~70%
Artificial	~40%
Organic	~75%
Natural	~65%
Artificial	~30%

7.1.2. Product 2 (RID® Shampoo)

Sponsor: OYSTERSHELL

Name of main investigator: [name]

Phone number in case of emergency: [name]

Clinical trial ref.: OYS007-0017

Subject n#: XXX

Use / zone: Topical use on hair and scalp

Posology: First treatment: D0; second treatment: D7

Storage: Store at room temperature, keep out of sunlight, close bottle tightly, shake well before use.

For personal use

7.2. Product identity

The test product X92001666 and the lice comb will be supplied by Oystershell Laboratories. The reference product will be purchased by the study center. All investigational products must be stored away from sunlight in a locked area at room temperature. Maintenance of a temperature log (manual or automated) is expected. The following samples of the investigational products have been chosen for the study:

	Investigational Product	Comparative Product
Product Name:	Water-soluble head lice suffocation product (X92001666) - Elimax Ultra®	RID® Shampoo
Dosage form:	Two-phase, water-based lotion	Shampoo
Active Ingredient Concentration Bottle size	[REDACTED] 3.4 oz. bottle	Pyrethrum 2 or 4 oz. bottle
Route of Administration:	Topical – hair & scalp	Topical – hair & scalp
Formula preparation and dosing instructions	
 [REDACTED] [REDACTED] [REDACTED] Apply on dry hair and spread until hair and scalp are fully saturated. After 15 (+2) min exposure, wash the hair with Johnson Baby shampoo. Dry the hair thoroughly with a towel (no hair dryer). 	
 Saturate on dry hair with Rid shampoo (see below) and treat for 10 (+2 min); rinse with warm water and then towel dry (no hair dryer). 
 Short hair: 2 oz. Shoulder-length: up to 3 oz. Mid-back hair: 4 oz.
Manufacturer	Oystershell NV	Bayer Group

7.3. Product administration / documentation

Subjects will have the test product applied on the initial visit by the investigative site personnel after it has been determined they are eligible for the study. The date and start time of the application of the test product will be recorded as well as the time the hair is considered dry. The Investigator, or their delegate, is responsible for study treatment accountability, reconciliation, and record maintenance.

The Investigator or their delegate must maintain study treatment accountability records throughout the course of the study. The responsible person(s) will document the amount of test product received from and returned to the sponsor and the amount supplied and/or administered to subjects. The required accountability unit for this study will be by weight by bottle (weight is to be recorded pre-application and post-application to the subject). Discrepancies are to be reconciled or resolved.

The use and fate of investigational products must be documented. After completion of the study, the containers including any remaining investigational product will be orderly destroyed by the study center. A written explanation regarding the disposition of missing products or their containers is required.

7.4. Assessment of Compliance

Subjects are to be dosed at the study site; they will receive study treatment directly from the investigator or designee, under medical supervision. The date and time of each dose administered/applied in the clinic

will be recorded in the source documents. The dose of test product and study participant identification will be confirmed at the time of dosing by a member of the study site staff other than the person administering/applying the test product.

7.5. Product – Instructions for Use

In this study, the individual dose is chosen, according to the leaflet or the instruction of use.

7.5.1. Test product (X92001666; Elimax Ultra®)

The test product will be evenly dispensed (massage) in the hair over its full length, with special diligence on the base of the hair near the scalp (full saturation is essential). After 15 minutes without covering the hair, the hair is washed with Johnson's Baby. A deviation up to plus 2 minutes due to organizational reasons, particularly to deal with children's ability to follow strict procedures, will be accepted. Consequently, the shampoo is rinsed thoroughly with a sufficient amount of water. Afterwards, the hair will be towel-dried (no hair dryer), detangled with a normal comb and finally, combed with the lice comb. Hair is parted into three sections and one section at a time is combed, starting at top of the head and placing teeth to scalp as close as possible. The hair is combed 6x from the scalp to the end of the hair. Following combing, hair and scalp are checked for head lice and nits.

WARNING: Do not smoke during product use. Keep away treated hair from fire, flames and ignition sources.

7.5.2. Reference product (RID® shampoo)

Subjects with short hair will receive approximately 60 mL (2 oz.), while subjects with shoulder length-hair will receive up to 90 mL (3 oz.). Subjects with shoulder length hair from the subject's shoulder until the mid-back hair will be treated with about 120 mL (4 oz.) of the product. No more of the investigational products will be used, as necessary to properly cover the hair and scalp.

The reference product will be evenly dispensed (massage) in the hair over its full length, with special diligence on the base of the hair near the scalp (full saturation is essential). After 10 (+ 2) minutes, warm water is applied to form a lather. Consequently, the hair is rinsed thoroughly to remove foam and residual product. Afterwards, the hair will be towel-dried (no hair dryer), detangled with a normal comb and finally, combed with the lice comb 6x. Place comb as close to scalp as possible and comb with a firm, even motion away from scalp, starting from the roots of the hair.

The applied amount of both investigational products will be documented for each subject in the CRF.

WARNING: Do not smoke during product use. Keep away treated hair from fire, flames and ignition sources.

8. STUDY POPULATION

8.1. Number of Subjects

In total, 70 subjects ages 2+ years and older will be enrolled in the study. Based on previous clinical data with comparable head lice products, a power analysis has been performed. Results indicated that a sample size of 35 subjects in each treatment group results in a power of 80%, considering a cure rate of 95% for

the test product and 55% for the reference product and a superiority margin of 15%. In case of dropouts, subjects will not be replaced.

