5. OBJECTIVES & ENDPOINTS

5.1. Primary objective

The primary objective of this study is to demonstrate that the cure rate after local application of test product is better than a predefined limit. The test product must achieve a cure rate superior to 70% (at the end of day 10, corrected for re-infestation).

To compare efficacy and safety of test product against reference product in subjects, infested with head lice (*Pediculus humanus capitis*).

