10.1. Sample size determination

Based on previous clinical data with comparable head lice products, a power analysis has been performed. Results indicated that a sample size of 30 subjects in both treatment groups result in a power of 80%.

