10.2. Data Analysis Considerations

Based on previous clinical data with comparable head lice products, a power analysis has been performed. In order to detect superiority (superiority margin of 15%) of the test product (cure rate of 95%) over the reference product (cure rate 55%) with a power of 80% at 5% level of significance, 30 subjects are needed per treatment group.

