10.4. Efficacy Analyses

Efficacy analyses will be performed on the ITT population, consisting of all subjects who were included and randomized in the study, with available baseline value of the primary endpoint and at least one follow-up visit for the efficacy parameters. All statistical test will be performed at a 5% level of significance.

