10.4.1. Analysis of primary objective

The cure rate (p) corresponds to the proportion of subjects who are cured at day 10 among all subjects that received any treatment at day 0. The aim of the study is to show superiority for the cure rate of the test product versus a predefined limit of 70%.

The following null hypothesis will be tested:

$$H_{0, \text{prim}}: p_T - p_R = 0 \text{ and } H_a: p_T - p_R > 15\%$$

A χ^2 -test of independence will be used to test the null hypothesis.

In case superiority could not be proven, non-inferiority will be tested. According to ICH guideline “Points to consider on switching between superiority and non-inferiority” [17], it is allowed to assess non-inferiority in to the absence of superiority. Prerequisites include:

- predefinition of a non-inferiority margin
- no correction in terms of multiplicity

As non-inferiority margin (δ), a 7.5% worse cure rate is regarded as clinically not relevant. The following null hypothesis will be used: $H_{0, \text{NI}}: p_T - p_R < \delta$, whereby $\delta = -7.5\%$. The lower, 95% confidence interval (CI) of the difference $p_T - p_R$ will be used for the test. If $H_{0, \text{NI}}$ will be rejected, non-inferiority cannot be shown.

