19.1. Subject Withdrawal Procedures

If a subject is prematurely withdrawn from study participation for any reason, the Investigator must make every effort have the subject return to the clinic for a final evaluation. Subjects that withdraw early from

the study for any reason may be replaced with another subject to meet the original target of 50 subjects to complete the study.

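### Sections 8.1 and 10.2 give 35 and 30 per arm for the same 80% power, with no test, sidedness or variance method that fixes which applies; 19.1 conflicts with 8.1 and 8.4.4 on target and replacement

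*Combined protocol and SAP*

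**What the plan says.** Three sections of the protocol justify the sample size.

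- Section 8.1 plans 70 subjects and says "Results indicated that a sample size of 35 subjects in each treatment group results in a power of 80" per cent, for cure rates of 95% (test) and 55% (reference) and a superiority margin of 15%. It gives no significance level.
- Section 10.1 says "Results indicated that a sample size of 30 subjects in both treatment groups result in a power of 80" per cent and gives no inputs.
- Section 10.2 repeats the rates and margin of 8.1 and concludes "with a power of 80% at 5% level of significance, 30 subjects are needed per treatment group".

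On the level, section 10.4 says only "All statistical test will be performed at a 5% level of significance". One- or two-sided is not stated anywhere, and neither is a variance method or an expected drop-out rate.

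On the analysis, section 10.4.1 opens with "The aim of the study is to show superiority for the cure rate of the test product versus a predefined limit of 70" per cent, in line with section 5.1 ("The test product must achieve a cure rate superior to 70" per cent). It then writes a null hypothesis of zero difference between the arms, with an alternative of a difference above 15%, and says a chi-square "test of independence will be used to test the null hypothesis". Non-inferiority with a 7.5-point margin follows if superiority is not shown. No test is named for the comparison with 70%.

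On enrolment, sections 6.1, 8.1 and 8.2 all give 70 subjects, and 8.1 and 8.4.4 rule out replacement. Section 19.1 says subjects who withdraw "may be replaced with another subject to meet the original target of 50 subjects to complete the study".

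**The concern.** Two different sample sizes are offered as the answer to one calculation. Sections 8.1 and 10.2 share both rates, the margin and the power, yet differ by five subjects per arm, and nothing in the text explains the gap. A reader therefore cannot tell which test and level the trial was sized for, and cannot check the claim of 80%.

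Sidedness decides whether that claim is true at all. If the 5% is read as two-sided, a test against the 15-point margin falls short of 80% at both sizes.

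The test that was sized is also not the test that was written. A sample-size statement should give the power of the planned analysis; here it gives the power of a margin test, while 10.4.1 specifies a test of zero difference and an aim against a fixed 70%.

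The conflict over replacement is practical. A site following 19.1 and a site following 8.4.4 would handle the same withdrawal differently, and the point at which enrolment ends is not fixed.

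**Working it through.** **Inputs.** Test rate 0.95, reference rate 0.55, margin 0.15, power 80% (8.1 and 10.2); level 5% (10.2 and 10.4), sidedness unstated; allocation 1:1 (6.1). The effect beyond the margin is 0.95 − 0.55 − 0.15 = 0.25.

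**Variances.**
- Unpooled: 0.95×0.05 + 0.55×0.45 = 0.295.
- Pooled null, mean rate 0.75: 2×0.75×0.25 = 0.375.

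**Reproducing 30 (10.1, 10.2).** With unpooled variance at one-sided 5%:
n = (1.645 + 0.842)² × 0.295 / 0.25² = 29.2, rounded up to 30.

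**Reproducing 35 (8.1).** With pooled null variance at one-sided 5%:
n = (1.645×√0.375 + 0.842×√0.295)² / 0.25² = 34.3, rounded up to 35.

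**Power of the margin test at each size.**
- Unpooled: Φ(0.25×√(n/0.295) − z)
- Pooled: Φ((0.25×√n − z×√0.375)/√0.295)

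| Level | Variance | 30 per arm | 35 per arm | n for 80% |
|---|---|---|---|---|
| One-sided 5% (z = 1.645) | unpooled | 81.0% | 86.0% | 29.2 → 30 |
| One-sided 5% | pooled null | 74.7% | 80.7% | 34.3 → 35 |
| Two-sided 5% (z = 1.960) | unpooled | 71.3% | 77.7% | 37.0 → 38 |
| Two-sided 5% | pooled null | 62.2% | 69.6% | 43.9 → 44 |

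Neither formula gives both 30 and 35. Exact enumeration of the unpooled test agrees with the first and third rows (80.7% and 86.2% one-sided; 70.7% and 77.6% two-sided).

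**Other routes tried.** A variance restricted to the null gives 31.4 per arm at one-sided 5%, which fits neither figure. A continuity correction at one-sided 5% gives 34 to 37, near 35. If 35 is 30 inflated for drop-out, the implied loss is 1 − 30/35 = 14.3%. The documents give no rate, so this is an assumption. At two-sided 5% every variant tried needs at least 37.0 per arm before rounding.

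**Power of what 10.4.1 writes, at 95% and 55%.**

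| Analysis | 30 per arm | 35 per arm |
|---|---|---|
| Chi-square of zero difference, two-sided 5%, exact enumeration | 97.7% | 99.0% |
| Same, with continuity correction | 95.3% | 98.0% |
| Test arm against 70%, exact binomial, one-sided 5% (at least 26/30 or 30/35 cured) | 98.4% | 99.3% |
| Same, one-sided 2.5% (at least 27/30 or 31/35 cured) | 93.9% | 97.1% |

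The exact binomial is an assumption, since no test is named. Non-inferiority at 7.5 points has above 99.7% power at either size. None of these is 80%.

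**The 50-completer target.** Split equally (an assumption), 50 is 25 per arm. The unpooled margin test at one-sided 5% then has Φ(0.25×√(25/0.295) − 1.645) = 74.4%. Fifty matches neither 2×30 = 60 nor 2×35 = 70.

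**The case against.** The strongest reply is that neither figure is an arithmetical error. Thirty follows from one common formula and 35 from another, or 35 may be 30 plus an allowance for loss. That stands. A reader who uses the unpooled formula might infer that 30 is verified and 35 is the mistake, because that formula gives 86% at 35. The documents do not support this: they name no formula, and with pooled variance 35 is confirmed and 30 falls to 75%. What survives is that 8.1 ties the 80% to 35 and 10.2 ties it to 30, with nothing to connect them.

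A reader might also infer that the 15-point margin is absent from the analysis. It is not: the alternative hypothesis in 10.4.1 names it. The narrower point holds, because the null is zero difference and a chi-square test of independence tests that null without a margin.

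A third inference would be that the trial is too small. At the assumed rates the written analyses have ample power at 30 or 35 per arm. The shortfall is conditional: it arises only if the 15-point margin is tested at two-sided 5%.

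Finally, 50 completers could be read as a floor beneath 70 enrolled, and 70 is stated consistently in 6.1, 8.1 and 8.2. Even so, permitting replacement in 19.1 cannot be squared with ruling it out in 8.1 and 8.4.4.

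**Conclusion.** The point holds as a fault in the stated figures and rules. For identical rates, margin and power, the plan gives two sample sizes. Of the variants tried, each is reproduced only at an undeclared one-sided 5%, and by a different variance formula. At two-sided 5% the claimed 80% is missed by 2 to 9 points with unpooled variance and by 10 to 18 points with pooled variance. The 80% describes neither the chi-square test nor the comparison with 70%, whose power is about 94–99%. The replacement rule and completer target in 19.1 contradict 8.1 and 8.4.4.

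These figures rest on the plan's own cure rates, on complete data at the stated sizes, and on an exact binomial test for the 70% limit. Identity of inputs is established between 8.1 and 10.2 only; 8.1 omits the level and 10.1 omits the inputs. How 35 arose cannot be determined from the documents. The contradictions are certain, their effect on the trial's power is modest, and correction is advisable.

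**What to change.** Put one sample-size statement in 8.1, 10.1 and 10.2. It should name the test, the margin, the sidedness, the variance method and any drop-out allowance with its rate, and agree with the test specified in 10.4.1. At the planned 35 per arm, the matching power of the margin test is 86% (unpooled) or 81% (pooled) at one-sided 5%, and 78% or 70% at two-sided 5%. If 35 is 30 plus an allowance for loss, say so.

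Add the power of the comparison with 70% at 35 per arm: 99% at one-sided 5% or 97% at one-sided 2.5%, if an exact binomial test is adopted.

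Reconcile the completer target and replacement rule in 19.1 with 8.1 and 8.4.4, so that one enrolment target and one rule appear throughout.

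The cost is a text correction, and enrolment need not change. The downside is that, if the margin test is declared two-sided, the plan must state a power below 80%. Keeping 80% in that case would take 38 per arm (unpooled) or 44 (pooled).

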8.2. Method of assigning volunteers to treatment groups / randomisation

Subjects who meet the inclusion criteria will be randomized to receive test product or reference product. Randomisation will be performed during the screening visit V1 on day 0. A block randomisation (block sizes of 2) will be performed by the external statistician using statistical software (R version 3.4.2; R development core team, 2017). The randomization schedule will be send to the sites prior to study conduct. All subjects will be enrolled into the study, sequentially beginning with Subject Number 1-70.

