6.2. Screening/Treatment Day (Day 0)

Subjects with suspicion of head lice infestation will be recruited for this study. Written informed consent will be obtained from adult subjects or the legal representative of minors. Children, must give their assent in written. The assent of younger children will be given verbally as far as appropriate. Subject's eligibility for participation in the trial will be established by the investigator prior to enrolment. Screening assessments will include recording of demographic data, medical history and current medication usage, an assessment of the head, scalp and eyes, vital signs, and a urine pregnancy test in females of child-bearing potential. A subject must meet all inclusion criteria, and none of the exclusion criteria, to be eligible.

Diagnosis of a head lice infestation will be confirmed by identification of at least five living adult head lice or nymphs and five apparently live eggs. The severity of the infestation will be judged on a 4-point severity scale:

- 0 = no relevant infestation (0-4 lice and/or nymph present)
- 1 = mild (5-9 lice and/or nymphs present)
- 2 = moderate (10-24 lice and/or nymphs present)
- 3 = severe (≥ 25 lice and/or nymphs present)

Subjects who meet the inclusion criteria will be randomized to receive test product or reference product. Prior to the study, a block randomisation (block sizes of 2) will be performed by the external statistician using statistical software (R version 3.4.2; R-development core team, 2017). The randomization schedule will be send to the sites prior to study conduct. All subjects will be enrolled into the study sequentially beginning with Subject Number 1-70.

Following the instructions for use, subjects will have the test product applied by clinic personnel to ensure consistent application and consequently combed with a lice comb (also see chapter 7). Date and times of start and end of application of the investigational product and times of tolerability and efficacy assessments will be documented. Post-treatment assessments will be performed directly after start of treatment, as well as 1 hour after removing the investigational product. This will be considered Day 0 of the study.

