8.3. Blinding

As both products are substantially different from each other in terms of packaging, smell and application method, it is not possible to do a double-blinded trial. Both, the subjects and the clinic personnel that will apply the investigational products, will be able to recognize the products. Therefore, an investigator-blinded study will be performed, and an independent assessor (investigator or study staff performing the assessments of hair and scalp, eyes, as well the efficacy and safety evaluations) will be blinded to the treatment. Appropriate measures will be taken to keep the assessor blind during the whole study. The assessor will not be involved in any procedure of the trial involving the handling, storage, and use of the products.

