8.6.2. Exclusion Criteria

Deviations from exclusion criteria are not allowed because they can potentially jeopardize the scientific integrity of the study, regulatory acceptability or subject safety. Therefore, adherence to the criteria as specified in the protocol is essential.

A subject will not be eligible for inclusion in this study if any of the following criteria apply:

1. Application of any form of head lice treatment, whether prescription or over-the-counter (OTC), or home remedy for 30 days prior to their screening visit (Day 1).
2. Application of any topical medication of any kind on the hair for a period of 48 hours prior to the screening visit.
3. Use of systemic or topical drugs or medications, including systemic antibiotics, which in the opinion of the investigative personnel may interfere with the study results.
4. Known skin allergies, multiple drug allergies or multiple allergies to cosmetic products.
5. History of allergy or hypersensitivity to ragweed, active ingredients or constituents of the test products.
6. Subject with any visible skin/scalp condition at the treatment site which, in the opinion of the investigative personnel, will interfere with the evaluation of the test product.
7. Subjects with chronic scalp disorder.
8. Subject or his/her legal guardian who, in the opinion of the investigative personnel, do not understand the subject requirements for study participations and/or may be likely to exhibit poor compliance with the required visits.
9. Females who are pregnant or nursing.
10. Hair longer than mid-back.
11. Subject suspected or known not to follow instructions
12. Previous participation in this study or participation in any other investigational trial within the preceding 30 days
13. The subject is directly affiliated to the investigator site personnel and/or their immediate families. Immediate family is defined as a spouse, parent, child, or sibling, whether biological or legally adopted
14. The subject is an Oystershell employee or is an employee of a third-party organizations involved in the study.

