9.4.8. Assessment of the hair and scalp (diagnostic combing)

An assessment of the hair and scalp will be performed to determine the number of live lice in the hair with a special lice comb (dry combing). The lice comb will be provided by Oystershell (OYS internal code: 07080019).

For this assessment, the hair will be divided into 3 sections: left, middle, and right side of the head. Each section will be combed 6x with a lice comb and the number of live lice encountered per section is recorded. The hair will be assessed for lice on day 0 to determine if the subject complies with the inclusion criterion: ≥ 5 live lice. This procedure will be repeated for all visits before and after treatment.

The life stage of lice found during assessments on all visits must be recorded as this is necessary for determination of re-infestation (see chapter 9.5). In case that the examination on day 1, 2, 7 or day 10 will show active head lice infestation, the lice caught by the comb will be discarded. The subjects with active head lice infestation on day 10 will be considered a treatment failure and will receive an appropriate treatment.

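### Blocks of 2 are printed in the protocol and the schedule goes to the sites with no concealed release described, so up to half the allocations can be foreseen from earlier ones, and all of them by anyone holding the list

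*Combined protocol and SAP*

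**What the plan says.** Section 8.2 reads "A block randomisation (block sizes of 2) will be performed by the external statistician" and "The randomization schedule will be send to the sites prior to study conduct". Section 6.2 repeats both points. Both sections number subjects 1 to 70 in sequence, and section 6.1 allocates those numbers in ascending order of inclusion, 1:1, at two centres. How the numbers are divided between the centres is not stated. No section mentions envelopes, a central or web system, or an independent holder of the list. Section 9.8 names the random list among the source documents, and gives the subject file as a possible source for both the randomisation entry and the lice count.

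On who knows what, section 8.3 says that subjects and applying personnel "will be able to recognize the products". It makes the assessor of hair, scalp and eyes, who may be the investigator or study staff, blind to treatment, and promises unspecified measures to keep the assessor blind throughout. It adds: "The assessor will not be involved in any procedure of the trial involving the handling, storage, and use of the products". The table in section 6.7 has a matching row, "Application of study medication by unblinded study staff".

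On enrolment, section 6.2 says that "eligibility for participation in the trial will be established by the investigator prior to enrolment". Section 9.4.8 uses the day-0 combing "to determine if the subject complies with the inclusion criterion". Several exclusions in section 8.6.2 rest on judgement: nos. 3, 6 and 8 on the opinion of site personnel, and no. 11 on suspicion, "Subject suspected or known not to follow instructions".

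**The concern.** With a fixed block of 2, the second allocation in each block is the opposite of the first. Because the block size is printed and the products are recognisable, a staff member who knows what the last subject received can often state what the next will receive. With the schedule in hand, nothing needs to be inferred.

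Two things are at stake. First, if the person who signs off eligibility can foresee the next allocation, a borderline subject can be accepted, declined or delayed with the arm in mind. Randomisation would then no longer protect the comparison between arms, or the make-up of the test arm that section 5.1 judges against 70%. Secondly, assessor blinding is the only blinding in this trial. With blocks of 2, an assessor who learns one subject's product also knows that of the block partner.

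**Working it through.** The plan gives no predictability figure to reproduce, so the check starts from its design inputs: 70 subjects, 1:1, two centres (section 6.1) and block size 2 (sections 6.2 and 8.2).

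**One list, all earlier allocations known.** 70 / 2 = 35 blocks, and the second place in each is determined by the first.
- Certain: 35 of 70 = 50%.
- Expected correct guesses: 35 × 1 + 35 × 0.5 = 52.5 of 70 = 75%.

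**Two separate lists of 35 (assumed split).** Each list holds 17 complete blocks and one unpaired number, so 17 + 17 = 34 are certain.

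**Schedule in hand.** 70 of 70 are known. The figure of 35 is therefore not an upper limit.

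**One shared list, each centre knowing only its own allocations.** Let q be one centre's share of enrolment, with subjects from the two centres arriving in random order. An allocation is certain if it is second in its block (probability 0.5) and its partner came from the same centre (probability q² + (1 − q)²). The documents do not give q, so these splits are assumptions:

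| Split | 0.5 × [q² + (1 − q)²] | Expected certain of 70 |
|---|---|---|
| 50:50 | 0.5 × 0.50 = 25% | 17.5 |
| 70:30 | 0.5 × 0.58 = 29% | 20.3 |
| 90:10 | 0.5 × 0.82 = 41% | 28.7 |

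**Would other blocks help?** The comparison assumes that the sizes have leaked and all earlier allocations on the list are known.

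| Design | Certain | Correctly guessed |
|---|---|---|
| Fixed 2 | 50% | 75% |
| Fixed 4 | 23.3 of 70 = 33% | 49.6 of 70 = 71% |
| Fixed 6 | 17.5 of 70 = 25% | 47.8 of 70 = 68% |
| Randomly varying 4 and 6, list of 35 per site | about 6% | about 69% |

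The fixed-block rows are exact if blocks fill completely. The last row is a simulation of 6,000 runs with a best-guess observer who knows the two sizes but not their order. Varying blocks remove most of the certainty but little of the overall guessability. Concealed release therefore matters more than block size.

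**What do varying blocks cost in balance?** In 40,000 simulated runs with two sites of 35 (assumed), the test arm had 34, 35 or 36 subjects in 24.7% + 48.5% + 24.8% = 98.0% of runs, and 33 or 37 in the remaining 2.0%.

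**The case against.** The plan has real safeguards. Section 6.2 places the criteria check and the inclusion decision before randomisation, and section 6.7 puts eligibility at −1 h and randomisation at 0. Section 8.3 calls the study investigator-blinded, bars the assessor from contact with the products and promises measures to keep the assessor blind. If the investigator who decides eligibility is that assessor, access to the list would break section 8.3. The day-0 lice count is itself a hair and scalp assessment under that section. Administration data have their own dispensing log (section 9.8), so the randomisation entry in the subject file need not reveal the product. Reasons for screening failure are recorded (sections 8.4.5 and 9.8), which leaves some audit trail.

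All of this stands, and it rules out saying that nothing protects the trial. It does not close the gap. Deciding eligibility first does not help if the next allocation is already foreseeable. The measures in section 8.3 are unspecified and concern the assessor. They do not say who may see the list, and no text ties the eligibility decision to the blinded assessor. An audit trail can show a pattern afterwards but does not prevent it, and section 21 keeps screen-failure data at the site.

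It is also fair to object that 35 of 70 is conditional: it needs one list and knowledge of every earlier allocation. The working gives the alternatives.

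A reader might infer that enrolling staff hold an open list, or that enrolment will be steered. The documents say only that the schedule goes to the sites; they do not say who holds it, and site procedures were not available. A reader might also infer that co-enrolled household members seriously distort the result, because sections 9.2 and 9.8 list household size but no linking identifier. That effect cannot be quantified, the CRF was not available, and new blocks would not keep housemates in the same arm.

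**Conclusion.** The concern holds as a gap in allocation concealment. As written, the scheme makes 35 of 70 allocations certain to anyone who knows all earlier ones on a single list, 34 with two lists of 35, and all 70 to anyone holding the schedule. On a shared list with only own-centre knowledge, the certain share runs from 25% to 41% over the assumed splits from 50:50 to 90:10.

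Selection bias and loss of assessor blinding are possible, not shown. The documents contain nothing from which to derive their size, so no figure for bias in the cure rate or in the difference between arms should be attached. Confidence is high for the gap in the text, and does not extend to its consequences. If a concealment procedure exists in a site document, it still needs to be stated in the protocol, and the block size still needs to come out of the copy that sites receive. This is a change that should be made; it does not invalidate the design.

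**What to change.** In sections 6.2 and 8.2, replace the sentences on block size, on sending the schedule and on numbering subjects 1 to 70 with:

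*The external statistician will generate a separate list per site, with site-specific subject number ranges and randomly varying block sizes recorded only in a document not available to the sites. Each allocation will be supplied in a sequentially numbered, sealed, opaque envelope held by the unblinded applicator and opened only after eligibility is confirmed in writing and the subject number assigned.*

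Blocks of 4 and 6 would serve. The numbering sentence has to change as well, because a single run of 1 to 70 does not fit separate site lists.

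In section 9.8, keep the random list and the product allocation out of any file used by the assessor or by the person deciding eligibility. In section 10.4, add a site-stratified sensitivity analysis (for example Cochran-Mantel-Haenszel), because separate lists stratify by site.

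The cost is two new lists, a set of envelopes and one supportive analysis. Sample size and main analysis are unchanged. The downside is the slight arm imbalance shown in the working.

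Optional and minor: add a household identifier to the CRF so that co-enrolled household members can be linked.
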